1.0 SYNOPSIS

Sponsor:	SciFluor Life Sciences, LLC [name] [name]
Protocol Number:	SF0166-C-001
Protocol Title:	A Phase I/II Randomized, Double-Masked, Multicenter Clinical Trial Designed to Evaluate the Safety and Exploratory Efficacy of SF0166 Topical Ophthalmic Solution in the Treatment of Diabetic Macular Edema
Investigational Product:	SF0166 Topical Ophthalmic Solution (SF0166)
Active Ingredient:	SF0166 ($\alpha_1\beta_3$ antagonists)
Number of Investigative Sites:	Approximately 10
Investigative Site Locations:	US
Number of Subjects:	Approximately 40 (20 in each arm)
Duration of Treatment:	28 days
Study Population:	Male and female subjects, aged 18 or older, with diabetic macular edema (i.e., retinal thickening secondary to type 1 or type 2 diabetes mellitus with DME with central subfield thickness ≥ 325 microns (μm) on spectral domain optical coherence tomography [OCT]) and no treatment with anti-vascular endothelial growth factor (VEGF) therapy within up to 60 days of study entry in the study eye
Objective(s):	To evaluate the safety and exploratory efficacy of SF0166 topical ophthalmic solution in patients with DME
Study Design & Methodology:	
This is a prospective, randomized, double-masked multicenter, Phase I/II clinical study in which approximately 40 eligible subjects with active DME will be randomized to 1 of 2 treatment arms in a 1:1 ratio as follows:
 
• SF0166 2.5% low dose twice daily (BID)• SF0166 5.0% high dose BID 
Randomization will be stratified by best-corrected visual acuity (BCVA) using Early Treatment Diabetic Retinopathy Study (ETDRS) testing (<40 letters versus ≥ 40 letters at Visit 1 – Screening/Randomization).
 
Eligibility and all site-related treatment decisions will be made based on Investigator assessment of OCT. All OCT images will also be reviewed by a central reading facility; however, eligibility is based on the Investigator's assessment at the time the

	
potential study subject is examined. The primary efficacy outcome is determined by the OCT assessments from the reading center.
 
Study subjects will administer the randomly assigned treatment for 28 days. There is an additional 28-day post-treatment follow-up period. All study subjects will return for examination every 2 weeks for 8 weeks (2 months).
 
Clinical assessments will include slit-lamp examination, intraocular pressure (IOP) measurement, BCVA, OCT, fluorescein angiography (FA), and fundus photography. Adverse events (AEs) will be recorded at all study visits.
 
Rescue therapy with a VEGF inhibitor can be administered to any study subject who experiences a significant decrease in BCVA, defined as BCVA loss of >7 letters from baseline (Visit 1 – Screening/Randomization), accompanied by an increase in OCT central subfield thickness of >75μm as compared to the previous study visit, as assessed by the Investigator.
 
Potential study participants will be asked to sign an informed consent document prior to screening. Once it is determined that all eligibility criteria have been met, subjects will be randomized to 1 of the 2 treatment arms. All study subjects and site staff will be masked to the treatment assignment.
 
The safety and exploratory efficacy of SF0166 will be evaluated over the course of the study. Since this is Phase I/II clinical study, no formal hypotheses testing is planned; descriptive statistics will be used to summarize the study outcomes.

Treatments:	
• SF0166 2.5% low dose BID• SF0166 5.0% high dose BID
Subject Selection:	
Inclusion Criteria:
 
1. Male or female, 18 years of age or older.2. Retinal thickening secondary to type 1 or type 2 diabetes mellitus with DME defined as central subfield thickness \geq325 μm on spectral domain OCT in the study eye.3. BCVA between 78 and 25 letters, inclusive, in the study eye at the screening/randomization visit using ETDRS testing, with BCVA decrement primarily attributable to DME.4. Treatment naïve (i.e., no previous anti-VEGF treatment in the study eye) or previously treated study eye with adequate washout defined below:
a. Lucentis (ranibizumab): 30-day washout

		
b. Avastin (bevacizumab): 30-day washoutc. Eylea (aflibercept): 60-day washoutd. Macugen (pegaptanib): 45-day washout5. Willing and able to return for all study visits.6. Able to adhere to the study dosing requirements.7. Understands and signs the written informed consent form.
	Exclusion Criteria:	
1. Active proliferative diabetic retinopathy (PDR) in the study eye, such as neovascularization of the optic disc (NVD), neovascularization elsewhere (NVE), vitreous hemorrhage, or neovascular glaucoma.2. Uncontrolled glaucoma or ocular hypertension in the study eye defined as an IOP >25 millimeter of mercury (mmHg) regardless of concomitant treatment with IOP-lowering medications.3. Uncontrolled hypertension defined as systolic >180 mmHg or >160 mmHg on 2 consecutive measurements (during the same visit) or diastolic >100 mmHg on optimal medical regimen.4. Screening glycated hemoglobin (HbA1c) blood test >12.0%.5. Previous panretinal photocoagulation (PRP) in the study eye within 4 months of study enrollment, or the need for PRP during the study based on the Investigator's opinion.6. Previous focal laser photocoagulation in the study eye, within the foveal avascular zone.7. Intravitreal/periocular/topical ocular steroids of any type in the study eye within 90 days (3 months) prior to study enrollment.8. Placement of Iluvien® or Retisert® (fluocinolone acetonide intravitreal implant) in the study eye within 36 months (3 years) prior to study enrollment.9. Use of Ozurdex® (dexamethasone intravitreal implant) in the study eye within 180 days (6 months) prior to study enrollment.10. Significant epiretinal membrane, posterior hyaloidal traction, and/or vitreomacular traction in the study eye as determined by the OCT results.11. Previous pars plana vitrectomy in the study eye.12. Any intraocular surgery in the study eye within 90 days (3 months) prior to study enrollment.13. Yttrium aluminium garnet (YAG) laser treatment

		
in the study eye within 30 days (1 month) prior to study enrollment.
 
14. Concomitant use of any topical ophthalmic medications in the study eye, including dry eye or glaucoma medications, unless on a stable dose for at least 90 days (3 months) prior to study enrollment and expected to stay on stable dose throughout study participation. Artificial tears are allowed.
 
15. High myopia in the study eye, with a spherical equivalent of >8.00 Diopters (D) at screening.
 
16. Chronic or recurrent uveitis in the study eye.
 
17. Ongoing ocular infection or inflammation in either eye.
 
18. A history of cataract surgery complicated by vitreous loss in the study eye.
 
19. Congenital eye malformations in the study eye.
 
20. A history of penetrating ocular trauma in the study eye.
 
21. Mentally handicapped.
 
22. Females of childbearing potential (i.e., who are not postmenopausal for at least 1 year or surgically sterile for at least 6 weeks prior to Visit 1 – Screening/Randomization) who are lactating, or who are pregnant as determined by a positive urine pregnancy test (UPT) at Visit 1 – Screening/Randomization. Women of childbearing potential must agree to use acceptable methods of birth control throughout the study. Acceptable methods of birth control include tubal ligation, transdermal patch, intrauterine devices/systems, oral/implantable/injectable or contraceptives, sexual abstinence, double barrier method, or vasectomized partner.
 
23. Participation in any other investigational device or drug clinical research study within 30 days of Visit 1 – Screening/Randomization.
 
24. Contraindication to the study medications or fluorescein dye.
 
25. Other ocular pathologies that in the Investigator's opinion would interfere with the subject's vision in the study eye.

Assessments:	• Spectral Domain OCT	

		
• Best Corrected Visual Acuity (ETDRS)• Slit-Lamp Biomicroscopy• IOP by Tonopen or Applanation• Indirect Ophthalmoscopy/Dilated Fundus Examination• Fundus Photography• Fluorescein Angiography• AEs
Outcomes:	Efficacy:	
The primary efficacy outcome is the mean change in anatomic center subfield thickness and macular volume, measured by OCT. All OCT images will be read by the Investigator and a central reading facility. The primary efficacy outcome is determined by the OCT assessments from the reading center.
 
The secondary efficacy outcome is the mean change from baseline in BCVA.

	Safety:	Safety parameters to be evaluated include BCVA, slit-lamp and fundus findings, IOP, and AEs.
Statistical Methods:	Descriptive statistics will be used to tabulate and summarize study outcomes. Background and demographic characteristics will be presented. Continuous variables will be summarized by descriptive statistics (sample size, mean and standard deviation, median, minimum and maximum). Discrete variables will be summarized by frequencies and percentages. Adverse events will be summarized by presenting the number and percentage of patients having any adverse event. Any other information collected (such as severity or relationship to investigational product) will be listed, as appropriate. Any statistical tests performed to explore the data will be used only to highlight any interesting comparisons that may warrant further consideration.	
Sample Size Justification:	Twenty subjects in each study arm are expected to provide an adequate sample size to distinguish any efficacy and safety differences between the dose groups.	

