8.0 SUBJECT POPULATION

The study population includes approximately 40 subjects, 18 years of age or older, randomized at approximately 10 sites. The goal is to enroll 40 subjects, 20 in each study arm, allowing for a minimum of 30 subjects to complete the study. To participate in the study, the subject must have center-involved diabetic macular edema (i.e., retinal thickening secondary to type 1 or type 2 diabetes mellitus with DME and central subfield thickness ≥ 325 μm on spectral domain OCT) in the study eye, either be treatment naïve or have been previously treated in the study eye with an adequate washout period (see [Sections 1.0](#) and [9.3](#)), achieve BCVA between 78 and 25 letters, inclusive, in the study eye using ETDRS testing, with BCVA decrement primarily attributable to DME, be willing able to attend all study visits and adhere to study regimen, and be willing to give written informed consent.

The duration of study participation is 8 weeks (± 2 days); including an on-treatment period of 28 days, and a post-treatment follow-up period of 28 days.

The complete inclusion and exclusion criteria are presented in [Section 1.0](#).

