9.3.2 Prohibited Treatments

Use of the following treatments is not allowed during the study and for the timeframes specified:

- Within 36 months (3 years) prior to study enrollment
 - Illuvien (fluocinolone acetonide intravitreal implant)
 - Retisert (fluocinolone acetonide intravitreal implant)
- Within 180 days (6 months) prior to study enrollment
 - Ozurdex (dexamethasone intravitreal implant)
- Within 90 days (3 months) prior to study enrollment
 - Focal laser photocoagulation or intravitreal/periocular/topical ocular steroids of any type in the study eye
 - Any intraocular surgery in the study eye
 - Any change in dose to a concomitant topical ophthalmic medication in the study eye
- Within 60 days (2 months) prior to study enrollment
 - Eylea (aflibercept) in the study eye
- Within 45 days prior to enrollment
 - Macugen (pegaptanib) in the study eye
- Within 30 days (1 month) prior to enrollment

- Lucentis (ranibizumab) in the study eye
- Avastin (bevacizumab) in the study eye
- YAG laser treatment in study eye

Subjects taking a stable dose of topical ophthalmic medications at study enrollment should be instructed not to dose study medication within 1 hour of investigational product dosing.

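### Exclusion 6 omits the 90-day focal-laser look-back in Section 9.3.2, so a recently lasered eye can meet every listed criterion and still breach the protocol (minor inconsistency)

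*Combined protocol and SAP*

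**What the plan says.** Exclusion 6 (Section 1.0) excludes "Previous focal laser photocoagulation in the study eye, within the foveal avascular zone". It is limited by location and not by time.

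Section 9.3.2 opens with "Use of the following treatments is not allowed during the study and for the timeframes specified". Its 90-day group includes "Focal laser photocoagulation or intravitreal/periocular/topical ocular steroids of any type in the study eye", with no restriction to a part of the retina. The same group lists "Any intraocular surgery in the study eye" as a separate item.

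The other two laser types in Section 1.0 each have a look-back. Exclusion 5 covers "Previous panretinal photocoagulation (PRP) in the study eye within 4 months of study enrollment", and Exclusion 13 covers YAG laser "in the study eye within 30 days (1 month) prior to study enrollment".

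Section 8.0 states that Section 1.0 holds the complete eligibility criteria. Under Section 9.2 and Visit 1 steps 8 and 9 (Section 10.1), a subject who meets those criteria is randomized through the IWRS. No Visit 1 step refers to 9.3.2.

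**The concern.** The two sections apply different rules to the same eye. The stricter one is in the concomitant-treatment section, and the criteria that trigger randomization carry only the looser one.

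Two things are at stake.

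- **The analysis set.** The primary population is Per Protocol (Section 11.1), which excludes subjects with significant deviations. An eye randomized under Exclusion 6 and later found to breach 9.3.2 is a deviation that clearer criteria would have prevented.
- **Interpretation.** The primary outcome is OCT change, and both arms receive SF0166. If recent laser changes retinal thickness during the study, that change appears as within-arm change on drug, and no vehicle arm is available to subtract it.

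**Working it through.** No formula in the plan bears on this, so the check is a comparison of texts followed by simple date arithmetic.

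**Step 1. Match each look-back item in 9.3.2 to Section 1.0.**

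| Item in 9.3.2 | Window | Counterpart in Section 1.0 |
|---|---|---|
| Iluvien | 36 months | Exclusion 8 |
| Retisert | 36 months | Exclusion 8 |
| Ozurdex | 180 days | Exclusion 9 |
| Ocular steroids | 90 days | Exclusion 7 |
| Intraocular surgery | 90 days | Exclusion 12 |
| Topical dose change | 90 days | Exclusion 14 |
| **Focal laser** | **90 days** | **none** |
| Aflibercept | 60 days | Inclusion 4c |
| Pegaptanib | 45 days | Inclusion 4d |
| Ranibizumab | 30 days | Inclusion 4a |
| Bevacizumab | 30 days | Inclusion 4b |
| YAG laser | 30 days | Exclusion 13 |

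That is 12 items, of which 11 have a counterpart; focal laser is the only one without. The steroid half of the same 9.3.2 bullet appears in Exclusion 7 with its 90 days, but the laser half was not carried over.

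**Step 2. Ask whether another criterion closes the gap.**

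- Exclusion 5 covers panretinal laser only, and Exclusion 13 covers YAG only.
- Exclusion 12 covers intraocular surgery. Section 9.3.2 lists surgery, focal laser and YAG as separate items and gives YAG its own window, so the protocol does not treat laser as surgery.
- Section 8.0 requires an eye to be treatment naïve or "previously treated in the study eye with an adequate washout period", and points to Sections 1.0 and 9.3. Inclusion 4 gives that phrase its meaning: "i.e., no previous anti-VEGF treatment in the study eye) or previously treated study eye with adequate washout defined below". The four washouts that follow are all for anti-VEGF agents.

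None of these catches recent focal laser outside the foveal avascular zone.

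**Step 3. Test case.** Focal laser outside the zone, 45 days before Visit 1. Exclusion 6 is not triggered because the location is outside the zone. Section 9.3.2 is breached because 45 < 90.

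**Step 4. Interval from laser to OCT.** Enrollment is taken as Visit 1 (Day 0), because screening and randomization are a single visit. Visits 3 and 5 are Day 28 ± 2 and Day 56 ± 2 (Section 2.0), so the earliest on-schedule scans are on Day 26 and Day 54. Interval = days from laser to Visit 1 + study day of the scan.

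| Rule or case | Earliest Visit 3 | Earliest Visit 5 |
|---|---|---|
| 9.3.2 (laser more than 90 days before) | more than 90 + 26 = 116 | more than 90 + 54 = 144 |
| Exclusion 6 alone, laser the day before Visit 1 | 1 + 26 = 27 | 1 + 54 = 55 |
| Exclusion 6 alone, laser 45 days before | 45 + 26 = 71 | 45 + 54 = 99 |

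The last two rows apply to laser outside the foveal avascular zone. An early-termination visit could fall sooner in any row.

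**The case against.** The strongest reply is that 9.3.2 already binds. It is part of the protocol, Section 6.0 requires compliance with the protocol, and Section 8.0 mentions Section 9.3. Visit 1 collects ocular history before eligibility is judged. A wrong enrollment therefore needs a site to overlook 9.3.2. This stands: the text permits the error but does not force it. The IWRS fields and any site checklist are not in the documents, so the frequency is unknown.

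The match in Step 1 is also not evidence that the lists otherwise mirror each other. Section 9.3.2 names the three steroid implants without limiting them to the study eye, while Exclusions 8 and 9 do limit them. Panretinal laser and vitrectomy are in Section 1.0 but absent from the 9.3.2 list. Focal laser is the only item with no counterpart, but it is not the only mismatch.

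A reader might infer more than the documents support:

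- **That the two rules contradict each other.** They do not. They are cumulative, and a site can satisfy both. The fault is an omission from the criteria.
- **That the sponsor meant to keep focal laser out altogether.** Both rules accept older laser outside the foveal avascular zone, and the bar on laser rescue in Section 10.7 concerns treatment during the study. Intent to keep recent laser out is a fair inference from 9.3.2, but no more.
- **That a 90-day window removes carry-over.** Section 5.0 says laser can be slow to act, over many months, and gives no timing specific to focal laser. Laser just over 90 days old remains allowed and could still be acting during the 56 days.
- **That the dose comparison is biased.** Allocation is randomized, so no systematic difference between doses is expected.
- **That the effect on the Per Protocol set can be quantified.** Any percentage for losing one eye would be the same for a removal for any reason, and the number of affected eyes is unknown.

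**Conclusion.** The inconsistency is real in the current text, and it is minor. As written, the rule for randomizing admits an eye that another section prohibits. The size that the text supports is the change in timing: the minimum interval from focal laser to the Visit 3 scan falls from more than 116 days to 27, and to the Visit 5 scan from more than 144 days to 55.

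Removal of such an eye from the Per Protocol set is possible but not automatic, because the study team judges the importance of deviations before database lock. The modified ITT set would keep any such subject who completed an on-treatment visit. No effect on the estimated OCT change can be given.

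This rests on reading Section 1.0 as the operative eligibility list, as Section 8.0 says, and on enrollment meaning Visit 1.

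**What to change.** Keep the foveal-avascular-zone exclusion without a time limit, and add a second limb to Exclusion 6 by amendment: *or any focal laser to the study eye, at any location, during the 90 days (3 months) before enrollment*. This is the protocol's own window, placed where eligibility is decided.

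If the sponsor did not intend that window, delete focal laser from the 90-day item in 9.3.2 and keep the ban on it during the study. Either way the two sections should agree.

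The cost is one clause. The first option may add a few screen failures. It would limit carry-over from laser but not exclude it.

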11.0 ANALYSIS PLAN

11.1 Analysis Data Sets

The primary analysis population will be the Per Protocol (PP) population, defined as all subjects who were randomized, completed the study as planned (i.e., after 28-day on-treatment period and 28-day follow-up period), and did not have significant protocol deviations. Protocol deviations will be reviewed by the study team and assessed for importance (i.e., the potential exclusion of a subject) prior to database lock.

The modified intent-to-treat (ITT) population will include subjects who were randomized and completed at least 1 on-IP study visit. The safety analysis set will include all randomized subjects.

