11.3.1.1 Statistical Hypotheses

Not applicable, as no formal hypothesis testing is planned.

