11.3.1.2 Analysis Methods

Both the Investigator assessed OCT values and the centrally read OCT values will be collected and analyzed. Descriptive statistics will be used to summarize the study outcomes. Continuous variables will be summarized by descriptive statistics (sample size, mean and standard deviation, median, minimum and maximum). Discrete variables will be summarized by frequencies and percentages. Any statistical tests performed to explore the data will be used only to highlight any interesting comparisons that may warrant further consideration.

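### The only sample-size rationale claims that 20 subjects per arm can distinguish any dose differences; no stated input supports this, and read literally the design cannot do it

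*Combined protocol and SAP*

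**What the plan says.** Section 1.0 (Synopsis), Sample Size Justification, states that twenty subjects per arm "are expected to provide an adequate sample size to distinguish any efficacy and safety differences between the dose groups". No other rationale is given. Section 8.0 repeats 40 subjects, 20 per arm, and adds an attrition allowance, "allowing for a minimum of 30 subjects to complete the study", but no reason for the number.

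The analysis is descriptive. The synopsis says "no formal hypotheses testing is planned; descriptive statistics will be used to summarize the study outcomes". Section 11.3.1.1 says of hypotheses: "Not applicable, as no formal hypothesis testing is planned". Sections 11.3.1.2 and 11.3.2.2 list sample size, mean, SD, median, minimum and maximum, plus frequencies and percentages for discrete variables. Neither lists a between-dose contrast or a confidence interval. Exploratory tests are allowed but "will be used only to highlight any interesting comparisons that may warrant further consideration".

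On who is analysed, Section 11.1 says: "The primary analysis population will be the Per Protocol (PP) population". That set is limited to subjects who completed treatment and follow-up and "did not have significant protocol deviations". Section 11.4 rules out replacing subjects who discontinue. For safety, Section 11.1 says: "The safety analysis set will include all randomized subjects".

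**The concern.** Both arms receive SF0166 (Section 12.6 notes that nobody is on inactive treatment), so low against high dose is the only randomized comparison. The sample-size sentence tells the reader that this comparison can be resolved, for efficacy and for safety. That is a statement about precision, and precision depends on variability, event rates and the number analysed. The protocol gives only the last of these.

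No dose-selection or success rule depends on the sentence. What is at stake is how the results are read. If the two arms look alike, a reader relying on the sentence could conclude that the doses do not differ, when the data may be compatible with a substantial difference either way. The planned summaries would not correct that impression, because they show each arm separately with no interval for the difference.

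**Working it through.** **Inputs from the protocol.** 20 per arm, 1:1 allocation (Section 1.0); a minimum of 30 completers (Section 8.0); Per Protocol primary set and all-randomized safety set (Section 11.1); no replacement (Section 11.4).

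**Assumptions of this review.** Two-sided 95% confidence, or 5% significance with 80% power; 30 completers split 15/15; unadjusted comparison of mean change with a common SD; adverse event rates of 10% and 20%.

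**1. Reproducing the plan's figure.** Twenty per arm cannot be reproduced, because there is no effect size, SD, event rate, error rate, power or precision target to put into a formula.

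**2. Precision of the difference in mean change, in SD units.** Half-width = t(0.975, n1+n2−2) × √(1/n1 + 1/n2).

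- 20/20: 2.024 × √(2/20) = 2.024 × 0.3162 = 0.640 SD
- 15/15: 2.048 × √(2/15) = 2.048 × 0.3651 = 0.748 SD
- 30 completers split unequally: 0.750 SD (16/14), 0.763 SD (18/12), 0.793 SD (20/10)

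Subjects with significant deviations also leave the Per Protocol set, so it could fall below 30 and the interval would then be wider.

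**3. Detectable difference.** The normal approximation is (1.960 + 0.842) × √(2/n): 0.886 SD at 20 per arm and 1.023 SD at 15. The noncentral t gives 0.909 SD and 1.060 SD. Power for a true difference of 0.5 SD is 34% at 20 per arm and 26% at 15.

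**4. Illustration in clinical units.** The protocol gives no SD of change, so these values are assumed. The half-width is the SD times 0.640 or 0.748.

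| Outcome | Assumed SD of change | 20 per arm | 15 per arm |
|---|---|---|---|
| Center subfield thickness (µm) | 50 / 100 / 150 | 32 / 64 / 96 | 37 / 75 / 112 |
| BCVA (letters) | 5 / 10 | 3.2 / 6.4 | 3.7 / 7.5 |

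**5. Between-dose difference in adverse event proportions, 20 per arm.** Approximate half-width = 1.96 × √(2p(1−p)/n).

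- p = 10%: 1.96 × √(0.18/20) = 0.186, about 19 percentage points
- p = 20%: 1.96 × √(0.32/20) = 0.248, about 25 percentage points

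This large-sample formula is rough at such counts (2 and 4 expected events per arm) and serves only to show the scale.

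**6. Zero-event limits.** The two-sided 95% upper limit is 1 − 0.025^(1/20) = 16.8% for 0/20 and 1 − 0.025^(1/40) = 8.8% for 0/40. These describe one dose group and the pooled trial. They do not measure a difference between doses.

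**The case against.** The strongest reply is that a descriptive Phase I/II study needs no power calculation, that the sentence states only an expectation, and that the protocol says repeatedly that nothing will be formally tested. This is right as far as it goes. Choosing 40 subjects is not a defect, and the descriptive framing limits the harm. But the protocol does not call the size pragmatic. It asserts a capability, and an expectation still needs a basis.

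A reader might infer more than the documents support:

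- *That the design is shown not to deliver what is claimed.* This follows only if *any* means however small, a standard that no finite trial meets. If it means whatever differences exist, adequacy depends on an SD and a relevant difference, and the protocol gives neither.
- *That only large dose differences could be distinguished.* In clinical units this depends on the SD. The one scale of notable change in the protocol is the rescue trigger in Section 10.7 (more than 7 letters lost with a thickness increase above 75 µm). It is a within-subject criterion, so only a loose guide for arm means. The half-widths above fall below it for some assumed SDs and exceed it for others. A half-width is also not a detectable difference.
- *That 0.64 SD is the best attainable.* It applies to an unadjusted 95% interval. Baseline adjustment could narrow it: if baseline and change correlated at an assumed 0.5, the factor is √(1−0.25) = 0.87, giving about 0.55 SD. No such model is planned.
- *That the sentence contradicts the descriptive plan.* Exploratory tests are permitted, so this is a tension only.

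**Conclusion.** The claim of adequacy is unsupported on either reading of *any*, because no input for it appears in the protocol. Read literally it also fails: steps 2, 3 and 5 show how far the resolution falls short of any difference, for efficacy and for safety. Those figures rest on the 95% level, the 80% power convention, the unadjusted comparison, the equal split of 30 completers and the assumed event rates.

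Whether this precision is clinically sufficient cannot be judged from the protocol, since no SD or relevant difference is stated. The finding therefore does not show that 40 subjects is the wrong number, and it alters no decision rule. It concerns a stated property that the design is not shown to have, together with an analysis that would report the only randomized comparison without its uncertainty. It is worth correcting.

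**What to change.** Keep 40 subjects. Replace the Sample Size Justification with wording such as:

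> The sample size is not based on a formal power calculation [sponsor to confirm the basis for N]. With 20 (15) evaluable subjects per arm, an unadjusted two-sided 95% confidence interval for the between-dose difference in mean change would have a half-width of about 0.64 (0.75) SD. For adverse events with a rate near 20%, the half-width for the between-dose difference with 20 per arm would be about 25 percentage points. Absence of an apparent difference will not be interpreted as evidence that the doses are equivalent.

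Add a descriptive 95% confidence interval for the between-dose difference in mean change to Sections 11.3.1.2 and 11.3.2.2 and to the synopsis Statistical Methods. If the sponsor can state expected SDs, give the half-widths in microns and letters too. If zero-event limits are wanted, label them as single-group (16.8%) and pooled (8.8%) safety precision.

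The cost is one replaced paragraph, the sponsor's confirmation of the basis for N, and one added descriptive interval in the two efficacy sections and the synopsis. Sample size, endpoints and conduct do not change. The downside is a less favourable statement of what the trial can show.
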